### **9.4.3. Analysis of Exploratory Efficacy Endpoints**

Exploratory endpoints include:

- For each of the five EQ-5D dimensions (Mobility, self-care, usual activities, pain/discomfort, anxiety/depression):
  - CMH RMS at Week 24
  - Using the Dichotomized values (No Problems vs Problems), a CMH general association analysis will be run at Week 24.
- Change from Baseline on EQ-5D Visual analogue score at Week 24
  - MMRM on observed data
- Change from Baseline on CSI score at Week 24
  - MMRM on observed data
- Change from Baseline on Likert scale (overall quality of sleep) at Week 24
  - MMRM on observed data
- Change from Baseline in sum of Parts D and E of the NPI at Week 24
  - MMRM on observed data

## 10. SAFETY AND TOLERABILITY

The safety analysis will be descriptive in nature, and will be presented for the Safety Population. All safety data collected and captured in the eCRF will be included in data listings sorted by domain, patient and time point, or as appropriate. Mean changes from pre-treatment to on-treatment (as well as post-treatment) will generally be tabulated by protocol-specified time points, while the number of patients with potentially clinically significant values at pre-treatment and at each endpoint will be presented. The last non-missing baseline value before dosing with the double-blind study medication will be used as the baseline value for that parameter. If a dose is taken on the same day as the assessments, the assessment will be assumed to be baseline.

Adverse events will be classified using MedDRA Version 18.1 coding dictionary. Tabulations will include an overall incidence of at least one adverse event, incidence within body system, and incidence by preferred term. Each patient may only contribute once (ie, first occurrence) to each of the incidence rates, regardless of the number of occurrences.

Generally, safety data will be presented for the Placebo Run-In Period, for the Double-Blind Treatment Period, and for the Post-Treatment (Follow-up) Period. AEs will be presented for the Screening period as well.

### 10.1. Adverse Events (AEs)

Adverse events will be tabulated by MedDRA system organ class (SOC) and preferred term, unless otherwise specified.

- Adverse events occurring prior to the first dose of single-blind study medication (ie, prior to the Placebo Run-In period) will be presented as Screening events.
- Adverse events occurring on or after the first dose of single-blind study medication but prior to the first dose of double-blind study medication will be presented as Placebo Run-In events.
- Adverse events occurring on or after the first dose of double-blind study medication, and within 7 days of the last dose of double-blind study medication, will be referred to as On-Treatment AEs (OTAEs).
- Events occurring after that will be presented as Post-Treatment. While the Post-Treatment period is defined as up to 30 days post-last-dose, it is possible some events may be reported that start after that 30 day period. These events will be included in the analysis.

Tabulations of the incidence of AEs will be presented as follows:

- Screening (using the Screening Population as the denominator).
- Single-Blind Placebo Run-In (using the Placebo Run-In Population as the denominator)
  - AEs
  - AEs resulting in discontinuation from study

- SAEs. SAEs will be tabulated (separately) as All SAEs, Non-Fatal SAEs and Fatal SAEs.
- Double-Blind Treatment Period (using the Safety Population as the denominator)
  - OTAEs. OTAEs will also be presented by the defined subgroups.
  - OTAEs occurring in  $\geq 5\%$  and  $10\%$  in EITHER Intepirdine treatment arm. These thresholds may be adjusted as the data dictate.
  - OTAEs judged by the investigator to be at least possibly related to study medication
  - OTAEs by maximum intensity (Grade 1 mild, Grade 2 moderate, and Grade 3 severe)
  - OTAEs resulting in discontinuation from study medication
  - SAEs. SAEs will be tabulated (separately) as All SAEs, Non-Fatal SAEs and Fatal SAEs.
  - SAEs judged by the investigator to be at least possibly related to study medication
  - An analysis of Adverse Reactions (defined as events occurring with higher incidence in either Intepirdine arm than in the Placebo arm) will be provided via a tabulation of these OTAEs.
- Post-Treatment Period (using the Safety Population as the denominator)
  - AEs
  - SAEs (Fatal and Non-Fatal)

A listing off deaths will be presented.

The time to first onset of OTAEs will be presented using the following bins of onset:

- 0 to 2 weeks
- >2 to 4 weeks
- >4 to 8 weeks
- >8 to 12 weeks
- >12 to 16 weeks
- >16 to 24 weeks
- >24 weeks

Time to first onset for select OTAEs may be presented via Kaplan-Meier plots and a log-rank statistic will be calculated (stratified by randomization baseline MMSE score). These events may include:

- OTAE resulting in discontinuation from study medication
- SAE

- Death
- Falls
  - SOC=Injury, poisoning, and procedural complications, PT=Fall.
  - The proportion of patients falling at any time will also be compared between the treatment groups using a CMH controlling for baseline stratification of MMSE and AChEI use.

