Study RVT-101-3001 was a 24-week, Phase 3 study that randomized 1315 subjects in a 1:1 ratio to receive placebo or 35 mg RVT-101 as an adjunct to stable donepezil treatment. The study utilized co-primary cognitive and functional endpoints at Week 24 (ADAS-Cog and ADCS-ADL) and a key secondary endpoint of global functioning at Week 24 (CIBIC+). When compared to placebo, a numerically superior difference of 0.36 points in ADAS-Cog was observed for the 35-mg RVT-101 group at Week 24, although it is not statistically significant ( $p=0.2249$ ). The functional endpoint of ADCS-ADL at Week 24 did not show much treatment difference (-0.09,  $p=0.8260$ ). For the key secondary endpoint of CIBIC+ at Week 24, statistically significant benefit versus placebo was demonstrated at Week 24 (-0.12,  $p=0.0234$ ). The treatment difference between 35 mg RVT-101 and placebo in CIBIC+ at Week 24 was largely consistent among subgroups of MMSE, age, sex, geographic region, and donepezil dose. In

addition, completer analysis, per protocol analysis and various sensitivity analyses using various statistical methods also showed statistical significance for CIBIC+ at Week 24.

RVT-101 is also being investigated in an ongoing, Phase 3, open-label, long-term extension to Study RVT-101-3001 (Study RVT-101-3002) and an ongoing, Phase 2b, long-term extension to this study RVT-101-2001 (Study RVT-101-2002). In addition, Axovant has assessed the tolerability and pharmacokinetics of multiple oral doses of 70 mg RVT-101 in a Phase 1 study (Study RVT-101-1001) and found the dose to be well-tolerated in elderly healthy subjects.

Details of all of the preclinical and clinical investigations with RVT-101 are contained in the current version of the RVT-101 Investigator's Brochure.

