**Safety Follow-Up:** All subjects who complete the Double-Blind Treatment Period and who do not enter the extension study will be required to attend a Safety Follow-Up clinic visit (Visit 13) 14 to 19 days after Visit 12.

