#### **8.3.2.1.3. Time Period and Frequency for Collecting Adverse Event and Serious Adverse Event Information**

Collection of AEs and SAEs will begin at the time a subject signs informed consent and continue until the follow-up visit. SAEs that are spontaneously reported by the subject or subject representative or discovered by the investigator or designee after the follow-up visit and up to 30 days after the last dose of IP must be collected and reported.

All SAEs will be recorded and reported to PPD or Axovant Sciences within 24 hours of the investigator becoming aware of the SAE.

Investigators are not obligated to actively seek AEs or SAEs in former study subjects. However, if the investigator learns of any SAE, including a death, at any time after a subject has been discharged from the study, and he/she considers the event reasonably related to the investigational product or study participation, the investigator must promptly notify the sponsor or sponsor representative.

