### 3. STUDY DESIGN

This is a multi-center, double-blind, randomized, placebo-controlled, parallel-group study in patients with probable DLB who are either not receiving therapy for DLB or are receiving a stable regimen of standard therapy for DLB. The efficacy and safety of Intepirdine at doses of 70 mg and 35 mg daily will be evaluated over a 24-week treatment period. All subjects who are on stable doses of other therapies to treat cognitive deficits and/or hallucinations associated with DLB will continue to remain on them for the duration of the study.

Approximately 240 subjects will be randomized. The randomization ratio will be 1:1:1 (70 mg Intepirdine: 35 mg Intepirdine: placebo). Double-blind treatment will be administered as follows:

- 70 mg Intepirdine (Test therapy): Intepirdine 70 mg given as two tablets of intepirdine 35 mg
- 35 mg Intepirdine (Test therapy): Intepirdine 35 mg given as one tablet of intepirdine 35 mg and one tablet of placebo
- Placebo (Reference): Matching placebo, given as two tablets of placebo

The primary endpoint (UPDRS Part III) and the secondary endpoints (ADAS Cog 11 and CIBIC+) will be measured after 24 weeks of treatment. Study participation will last approximately 32 weeks: 0 to 4 weeks for Screening, a 2-week Single-Blind Run-In Period to evaluate baseline status, a 24-week randomized, double-blind, placebo-controlled Treatment Period and a 2-week Safety Follow-up Period for subjects who do not enter the extension study RVT-101-2002.

[figure not shown]
There will be weekly clinical assessments for the first two weeks of double-blind treatment, bi-weekly assessments thereafter until 12 weeks post-randomization and every six weeks thereafter. For certain visits (Visits 5, 7 and 9), subjects may have the option of whether to have assessments performed at the clinical study site or by a trained, visiting nurse in their own home.

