An independent Safety Monitoring Committee (SMC) will review interim safety data accumulated after approximately 30 subjects have completed 4 weeks of double-blind treatment and throughout the study at points specified in the SMC Charter. The SMC will provide their recommendation regarding the acceptability of reducing the visit frequency by omitting certain visits (Visits 5, 7 and 9) for both newly enrolled subjects and subjects active in the study at the time of the recommendation. Study enrollment will not be stopped or slowed to wait for SMC's recommendation and will proceed as planned with all visits until the SMC recommendation is made. Site will be formally notified of the SMC's recommendation regarding whether Visits 5, 7 and 9 can be omitted. [The meeting did occur and the SMC recommended Visits 5, 7, and 9 be omitted.]

After completion of Visit 12, the subject may be considered for enrollment in the extension study RVT-101-2002. If the subject does not enter the extension study, he/she will return for the Safety Follow-up Visit (Visit 13). Subjects who enter the extension study will not be required to complete Visit 13.

A study schema is shown in [Figure 1](#) and study scheduled assessments are presented in [Table 2](#).

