#### **7.4. Analysis Populations**

It is intended that a complete accounting of patients for the analysis populations will be provided, from the Screening Population through the Per-Protocol Population.

- Screening Population: All patients who are screened (signed an informed consent) will be included in the Screening Population.
- Placebo Run-In Population: All patients who took at least 1 dose of IP in the Placebo Run-in will be included in the Placebo Run-In Population. This population will be used to provide an accounting of the disposition of patients during this phase of the study.

- Randomized Population: The Randomized Population will include all patients who are randomized.
- Safety Population: All subjects who were randomized and took at least one dose of double-blind investigational product.
- Intent-to-Treat (ITT) Population: All subjects randomized to treatment who have taken at least one dose of double-blind investigational product and who have a baseline and at least one post baseline primary efficacy assessment for the UPDRS-III **or** for the ADAS-Cog 11. This will be the primary population used for the efficacy analysis of all variables EXCEPT the UPDRS Part III and Part 5.
- UPDRS Primary Analysis Population: This will be the primary population used for the UPDRS Part III efficacy analysis, and is comprised of all ITT patients EXCLUDING those with no change OR a worsening in UPDRS-III total score prior to a dose increase in anti-parkinsonian medication (including but not limited to L-dopa, dopamine agonists, and monoamine oxidase inhibitors) and where there is *subsequent* improvement or stabilization of UPDRS-III total score.
  - Dose increase in anti-parkinsonian medication is defined as an increase in dose, dose frequency or commencement of anti-parkinsonian medication where the total daily dose of anti-parkinsonian medication at Week 24 is higher than at Baseline.
- UPDRS Sensitivity Analysis Population: All ITT patients EXCLUDING those who increase or start anti-parkinsonian medication treatment during the double-blind treatment period.
  - Dose increase in anti-parkinsonian medication is defined as an increase in dose or frequency or commencement of anti-parkinsonian medication where the total daily dose of anti-parkinsonian medication at Week 24 is higher than at Baseline.

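### Post-treatment AE and SAE percentages are divided by every dosed subject, including extension entrants who have no follow-up period, so the displayed rate depends on extension uptake

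*SAP*

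**What the plan says.** SAP 10.1 sets out the AE tables by study period. The last block is headed "Post-Treatment Period (using the Safety Population as the denominator" and covers both AEs and SAEs. SAP 7.4 defines that denominator: "Safety Population: All subjects who were randomized and took at least one dose of double-blind investigational product". It does not require any observation after treatment. In the same list in SAP 10.1, Screening events are divided by the Screening Population and run-in events by the Placebo Run-In Population.

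SAP section 3 describes a "2-week Safety Follow-up Period for subjects who do not enter the extension study RVT-101-2002" and adds: "Subjects who enter the extension study will not be required to complete Visit 13". Protocol 5.1 and 7.8 agree. On AE collection, Protocol 8.3.2.1.3 states: "Collection of AEs and SAEs will begin at the time a subject signs informed consent and continue until the follow-up visit". It also requires SAEs that come to light after that visit, up to 30 days after the last dose, to be reported.

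On windows, SAP 10.1 defines on-treatment events as "Adverse events occurring on or after the first dose of double-blind study medication, and within 7 days of the last dose of double-blind study medication". Later events are post-treatment, nominally up to 30 days after the last dose, and events starting later still are kept. Neither window mentions the extension. Protocol 3.1.2 lists, among ongoing studies of RVT-101, a "Phase 2b, long-term extension to this study RVT-101-2001 (Study RVT-101-2002"). It gives no dosing scheme or start date for it.

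**The concern.** An incidence percentage is read as a risk among people who could have shown the event. Here the numerator can come only from subjects who are observed after treatment, while the denominator also holds subjects for whom the design provides no such observation. The result mixes event risk with extension uptake.

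This matters in two ways. Within an arm, the follow-up table can make off-drug events look rarer than they were among the subjects followed. Between arms, two groups with the same risk can show different percentages simply because different shares rolled over. Entry to the extension is considered only after Visit 12 is completed, so a difference in discontinuation between arms can become a difference in rollover.

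A second gap lies in the windows. Because they do not end at the first extension dose, any event that this study records for a rollover subject after that dose would be tabulated under the originally randomized arm.

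**Working it through.** The documents give neither a post-treatment event rate nor a rollover rate, so there is no figure of the plan's own to reproduce. The check is how the stated rule behaves over a range of assumed values.

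**Inputs**
- N = 80 per arm (about 240 subjects randomized 1:1:1, SAP section 3).
- p = true post-treatment risk among followed subjects; 10% assumed.
- r = share of an arm entering RVT-101-2002; assumed, varied.
- c = share of rollover subjects with an event that this study captures after treatment; assumed, varied.

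**Formula.** Displayed rate = p × (1 − r) + c × r. This assumes that every non-rollover subject is followed.

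**Step 1: no rollover events captured (c = 0).** This is the natural reading for non-serious AEs, whose collection ends at a visit that rollover subjects do not have. The displayed rate is p(1 − r), so the understatement factor is 1/(1 − r). The last column takes 3 subjects with an event, which the SAP rule shows as 3/80 = 3.75% whatever r is.

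| r | Displayed when p = 10% | Factor | 3 events over subjects followed |
|---|---|---|---|
| 25% | 7.5% | 1.33 | 3/60 = 5.0% |
| 50% | 5.0% | 2.0 | 3/40 = 7.5% |
| 70% | 3.0% | 3.3 | 3/24 = 12.5% |
| 80% | 2.0% | 5.0 | 3/16 = 18.75% |

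**Step 2: arms with equal risk but unequal rollover (c = 0, p = 10% in both).**
- Rollover 60% on placebo and 80% on active: 0.10 × 0.4 = 4.0% against 0.10 × 0.2 = 2.0%, a ratio of 0.5 (active to placebo).
- The reverse: 2.0% against 4.0%, a ratio of 2.0.
- Equal rollover leaves the ratio at 1.0.

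The direction of any distortion follows the rollover pattern, which is unknown.

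**Step 3: some rollover events captured.** This is possible for SAEs under the 30-day rule. With r = 70% and p = 10%, the displayed rate is 3.0% + 0.7c:

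| c | Displayed |
|---|---|
| 2% | 3.0 + 1.4 = 4.4% |
| 5% | 3.0 + 3.5 = 6.5% |
| 10% | 3.0 + 7.0 = 10.0% |
| 20% | 3.0 + 14.0 = 17.0% |

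The displayed rate is too low when c < p, unchanged when c = p and too high when c > p. The two mechanisms act in opposite directions.

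**Step 4: who else is in the denominator.** Protocol 8.1 requires the follow-up visit of completers who do not enter the extension and times it as "Visit 13) 14 to 19 days after Visit 12". SAP Table 2 times the same visit from Visit 12 or early termination. Early terminators are in the Safety Population, but the documents disagree on whether they are followed. If some are not, the followed share is below 1 − r, and with c = 0 the understatement exceeds the factors in Step 1.

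**The case against.** The strongest reply is that the safety analysis is descriptive (SAP section 10), no test or decision rule uses this table, and a footnote giving the number followed would let a reader recompute the rate. The whole Safety Population also keeps the randomized groups intact, whereas a denominator of followed subjects is selected after randomization by completion and by choice. All of this stands. It limits the severity and belongs in the fix as a stated cost. It does not rescue the percentage as printed, because SAP 10.1 divides Screening and run-in events by the subjects who entered those periods and departs from that practice only here.

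The documents do not support four stronger readings that a reader might infer:
- **That all post-treatment rates are understated.** Step 3 shows that the direction depends on capture, and for SAEs the 30-day rule leaves capture open.
- **That active-drug events are being added to the placebo column.** The documents do not say what former placebo subjects receive in RVT-101-2002, when dosing starts, or which study's database holds their events. What is missing is a rule; an error has not been shown.
- **That this table is the only evidence on events after stopping drug.** The first 7 days off drug fall in the on-treatment tables, and Visit 13 also collects ECG, laboratory, vital-sign, C-SSRS and orthostasis data.
- **That rollover will differ because poor tolerators decline the extension.** The documents give no data on this. If it were so, followed subjects would also differ in risk between arms, and the equal-risk example in Step 2 would be only an illustration.

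**Conclusion.** The denominator rule in SAP 10.1 does not match the follow-up that the design provides. For non-serious AEs, rollover subjects count as event-free while unobserved, so the percentage falls as rollover rises and can differ between arms through rollover alone. The understatement is 2.0-fold at 50% rollover and 3.3-fold at 70%, on three assumptions: the rollover share itself, no captured rollover events, and follow-up of all other subjects. For SAEs the net direction is not established. The windows lack a stop at the first extension dose, so any captured event would sit under the original arm; whether such events arise cannot be told from these documents. Severity is low to moderate: the table is descriptive, and no primary or secondary efficacy inference depends on it.

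**What to change.** In SAP 10.1:
- Use as the post-treatment denominator the Safety Population subjects who did not enter RVT-101-2002 and have observation beyond last double-blind dose plus 7 days.
- Show the number followed and person-days per arm beside the Safety Population N.
- For subjects who roll over, end both the on-treatment (+7 day) and post-treatment windows at the first RVT-101-2002 dose, and list any later recorded events separately.
- State that the between-arm comparison in this table is descriptive only.

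Reconcile Protocol 8.1 with SAP Table 2 on whether early terminators have Visit 13, so that the followed group is defined.

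The cost is a few sentences of SAP text and a derived flag for the date of first extension dose. The price in interpretation is smaller denominators, wider uncertainty and a followed subset selected after randomization.

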## 10.2. Clinical Laboratory

Clinical laboratory parameters will be presented using three methods:

1. Tabulations of observed values over time. Group-mean plots (mean and standard error) over time will also be provided. Reference lines for the upper and lower normal values will be provided: where there are difference reference ranges for males and females, the highest (or lowest) value will be used as the reference line.
2. Tabulations of the incidence of potentially clinically significant (PCS) values by visits and at ANY TIME which includes 7 days after the date of the last dose of double-blind study medication. A focus will be on new-onset PCS values, ie, patients with pre-existing PCS values at pre-treatment will not be considered to have new-onset values on-treatment. For purposes of this analysis, the most extreme (highest and lowest) value AT ANY TIME for a parameter (for a given patient) will be used. Thus, a patient may contribute to both a low PCS value for a parameter as well as a high PCS value for that same parameter. PCS laboratory values are presented for serum chemistry in [Table 16](#) and for hematology in [Table 17](#).
3. Shifts from baseline to on-treatment, where values are categorized as low, normal, or high according to the lab normal values. For purposes of this analysis, the most extreme on-treatment values will be used (most extreme low and most extreme high). Shifts from baseline will be based on laboratory normal ranges as provided by the central laboratory.

In addition, the incidence of OTAEs relating to haematology and to serum chemistry laboratory parameters during the Double-Blind Treatment Period will be presented. These laboratory AEs will be identified from a review of the adverse events and select SOC and PTs will be included.

